## 5.2 Biomarkers (Circulating tumor cells)

Archived pathology specimens are clearly the most readily available human tumor samples, and antibody-based biomarkers amenable to immunohistochemical assays are desirable, but not easily converted from flow cytometry studies such as those described above. Efforts to correlate findings from an immunohistochemical analysis of CD44+24-10 expression have demonstrated the challenge in using a multi-marker biomarker.

In the absence of a single marker that can be applied to immunohistochemistry, Balic et al employed spectral imaging in conjunction with double marker immunohistochemistry to examine the simultaneous expression of CD44 and CD24 on cytokeratin-positive, disseminated tumor cells in the bone marrow of patients with early stage breast cancer. They reported that this was a technically feasible approach in these samples, and detected CD44+CD24-10 cells in all 50 samples with a median prevalence of 66%. The identification of this tumor-initiating phenotype on all cytokeratin positive disseminated tumor cells in the bone marrow raises interesting questions about the potential role for the detection of disseminated or circulating tumor cells as surrogate stem cell biomarkers. Circulating/disseminated tumor cells (C/DTCs) are tumor/epithelial cells in the blood or bone marrow of patients with breast cancer. In patients with metastatic breast cancer, the

presence of more than 5 of these cells in 7.5 mL of peripheral blood predicts for overall survival 20. These cells are detected by the presence of the epithelial cell marker CD326 (aka ESA or Ep-CAM), can be found in up to 30% of patients without known metastatic disease appreciated on standard staging studies even after systemic chemotherapy 21 and may predict for response to treatment 22. CTCs can be assayed in a standardized FDA approved assay and quantitated. In our own practice we have found that 75-90% of disseminated tumor cells in the bone marrow are CD44+24-/lo (unpublished data). More recent data has further refined the stem cell phenotype suggesting aldehyde dehydrogenase1 activity assayed as alde-fluor by flow cytometry yields greater selection of tumor initiating cells 23, and as such this single marker may be substituted for CD44+24lo studies.

### **5.3 CTCs as surrogate cancer stem cell markers**

The field of solid tumor stem cell biology has re-emerged at the forefront of clinical oncology in recent years due largely to the identification of new, prospectively identified stem/progenitor cell markers. Numerous putative markers are currently under investigation and considerable work is being done to identify new ones. This process is beset by two main challenges: how robust are the criteria used to validate the identified cell as a stem cell, and to what degree, under what conditions, and in which patients are identification of these cells reproducible? Thus far, prevailing observations across disease sites are that cancer stem cells are often basal cells, devoid of markers of differentiation such as hormone receptors, and can exhibit similar adhesion molecule profiles, CD44+, and more recently ALDH1. Commonalities among tumor-initiating cell surface markers have facilitated tumor-initiating cell identification in multiple tumor sites; however, the impact of tissue digestion on marker specificity inhibits the use of established cell surface stem cell markers on intact tissue sections or archived tissue. Cell surface molecules while ideal targets for FACS analysis, may not provide the optimal targets for IHC which are critical to widespread biomarker use.

[figure not shown]
The circulating tumor cell (CTC) population is an appealing cancer stem cell surrogate as these cells need not be subjected to digestion for evaluation, and appear to express the markers representative of tumor initiating cells (Figure 3, unpublished data; ARC-MD), hypothetically because they are indeed seeking a niche in which to sustain new disease foci. Prior and ongoing studies have established the feasibility of collecting CTCs in the randomized trial setting, and technology is emerging to facilitate systematic examination and quantitation of these cells. Recently, the U.S. Food and Drug Administration (FDA) approved an assay for the detection of circulating tumor cells in peripheral blood using a semi-automated system, the CellSearch system, and other approaches not yet approved by the FDA are under investigation.

The translational component of this study will correlate the change in CTCs with chemo-radiation treatment to change in expression the best putative stem/progenitor markers on digested tumor tissue. This will assess number of CTCs as a surrogate

endpoint for treatment of cancer stem cells, appropriately collect and store tissue and serum for future correlation of tumor stem cell markers to this endpoint, and set the stage for incorporation of targeted stem cells therapies in the treatment of locally advanced IBC and non-IBC. This component of the trial will be optional. Samples will be processed and analyzed by the IBC stem cell core lab ([name], and [name]).

**Figure 3.** Bone marrow isolated on IRB approved protocol from breast cancer patients undergoing surgery for primary tumor. Tumor cells identified by CD326+CD45- were assessed for stem cell phenotypes by flow cytometry

**Stem Cell Phenotypes in CD326+ BoneMarrow Cells**

%	% CD326 + CD45 lo	% CD44 + CD24 lo	%CD24 + CD29 +
Mean ± SEM	0.81 ± 0.07	76.3 ± 3.8	13.3 ± 2.4

## 6.0 Study Design

This is a single center, neoadjuvant phase II study (Schematic Appendix D). Eligible subjects must be women with a diagnosis of invasive breast cancer with primary or recurrent gross disease in the breast or chest wall or lymph nodes that is progressive, persistent, or minimally responsive to chemotherapy. Patients with oligometastatic disease (generally ≤ 3 distant sites, but at the discretion of the treating physician) who would benefit in terms of symptom palliation (pain, drainage, or emotional duress) are eligible. After the initial screening, patients who consent to translational studies will have the following samples stored or analyzed: serum (for CTCs, 1 tube – cell save; serum, 1 tube speckled top) and urine collection, and core needle biopsy (flow cytometry).

Size of tumor lesions in the breast and nodal basins will be documented based on initial clinical exam and imaging (planning CT) using recist criteria (Appendix F). All RECIST measurements will be made by a single physician, [name]. IBC status will be recorded. Palliative vs pre-operative intent (based both on extent of metastatic disease and primary disease) will be recorded by the treating physician (Initial Assessment Form Appendix G). Subsequently, eligible, consenting women will receive pre-operative radiation with concurrent capecitabine. Capecitabine is commercially available and the commercially available supply will be used. Neither the drug nor the radiation will be free. Patients receiving Herceptin (trastuzumab) are eligible for participation and may receive concurrent Herceptin plus radiation and Xeloda (capecitabine). Chemotherapy administered after protocol treatment (after the last dose of radiation and capecitabine) is acceptable. Surgical consultation or follow up will be requested to be scheduled after 45 Gy and before the final fraction of radiation for patients treated with pre-operative intent. The treating oncologist may change this status to palliative if the clinical course makes the surgical consult unnecessary/patient is clearly unresectable in the judgment of the treating oncologist.

After completion of 45 Gy and within 15 days of completing treatment the total protocol specified dose to the breast, in patients who consent to translational studies a second core needle biopsy (for banking and flow cytometry), serum (for CTCs, serum) and urine collection will be performed.

Linear accelerator based CT imaging (CT on rails or cone beam CT) or re-CT-simulation will be performed after 45 Gy to assess for the need to re-plan secondary to response. Tumor size will be documented using recist criteria based on these images. Additional accelerator based CT imaging is acceptable as clinically indicated.

Definitive or palliative local therapy with surgery when indicated will be performed after completion of the combined regimens. If the patient is deemed operable the first follow-up visit will occur after surgery. If the patient is deemed inoperable the first follow-up visit will occur after concurrent Capecitabine and radiation therapy. Subjects will be followed every 3 months (+/- 1 month) post treatment times 1, then every 6 months (+/- 1 months) times 1, then every 12 months (+/- 2 month) times 2. PET/CT scan or ultrasound will be performed in conjunction with the first follow up visit. For patients treated to definitive dose for gross unresected disease (any treatment field receiving a total of > 60 Gy in the mosaic prescription), all sites receiving > 60 Gy will be scored as complete response, partial response, noresponse/progressive disease based on imaging and exam after this visit and when evaluable and all subsequent visits. Subsequent radiologic studies will be at the discretion of the treating oncologist as dictated by standard of care. Toxicity will be recorded at each visit using the RTOG criteria.

Capecitabine dose reduction criteria are as follows:

Capecitabine will be held for patients experiencing grade 3-4 Capecitabine related

toxicities until symptomatic improvement (Grade 1). Radiation therapy will not be held for Capecitabine related toxicities. Patients will then be restarted with reduced dose of Capecitabine (level-1). Level -1 (25% dose reduction) = 600 mg/m^2 BID. If patients develop additional grade 3-4 toxicity in spite of dose reduction, the chemotherapy will be permanently discontinued.

Correlation will be made between Change in CTC level and change in percent of CD44+CD24lo or ALDH1+ cells in the tumor biopsy. Change will be correlated with clinical and pathologic response (in patients who undergo surgery)

Approximately 60 subjects will be enrolled. Assuming an average accrual rate of 3-4 subjects per month, the duration of accrual will be approximately 20 to 26 months.

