#### 9.1 During Radiation Treatment:

1. Locoregional disease progression.
2. Treatment is interrupted for more than 1 consecutive week.
3. An intercurrent illness, which would in the judgment of the Study Investigator, affect assessments of clinical status to a significant degree or require discontinuation of study treatment.
4. Nonprotocol therapy (chemotherapy) is administered during study treatment.
5. Non-compliance with protocol or treatment.
6. Refuses to continue treatment. Subject will undergo surgery; toxicity data will continue to be collected.

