# **11.0 Power Calculations and Statistical Analysis**

## **11.0 Power Calculations & Statistical Analysis**

### **11.1 Hypotheses**

The primary objective of this study is to determine response rate after completion of all protocol specified neoadjuvant chemotherapy+ concurrent radiation. The regimen will be considered of interest for further study if the response rate is at least 80% and the grade III toxicity excluding acute skin toxicity is <20%.

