### **11.3 Sample Size Considerations and Interim Analyses**

The primary objective of this study is to determine the efficacy of pre-operative radiation with concurrent capecitabine in patients who have experienced a minimal response or progression after standard neoadjuvant chemotherapy. Efficacy will be determined by tumour response (complete response + partial response) as measured by RECIST criteria. Tumour response will be assessed after 45 Gy. Those who do not finish will be considered non-responders. Toxicity will be assessed at the same time. Surgical complications will be assessed independently within 6 weeks of surgery. Only grade three toxicity will be considered in the stopping rules. This study will be monitored for both efficacy and safety. Safety will be determined by the rate of grade 3 or higher toxicities, excluding acute skin toxicity. This regimen will not be considered of interest for further study if there is a high probability that the response rate is less than 80% or the severe toxicity rate is greater than 20%. Priors regarding response are based on combined retrospective data from three studies of 135 total patients treated for gross disease in the breast at our institution and detailed in the background (sections 3.2 and 3.5). Local control (a surrogate for response) at 5-years in patients treated for gross IBC disease in the breast with radiation alone was 75% (N = 42, unpublished). In 38 similar patients with non-inflammatory breast cancer local control was 70% at 5 years. In an unpublished retrospective analysis of 55 patients treated with the regimen proposed herein, 5-year local control was 85% (Perkins, SABCS abstract, 2007). There are limited and poor data regarding radiation alone toxicity in this exact cohort. The priors for toxicity were based on aggressive xrt in post-mastectomy patients (N = 192). In these patients, we expect a 15% rate of Grade 3 toxicities in patients receiving 60Gy and a 29% rate of Grade 3 toxicities in patients receiving 66Gy, and unpublished data. Clinically we are currently limiting the use of the latter regimen based on the impression that this is unacceptably high toxicity, so we are targeting a Grade 3 toxicity rate of no more than 20%. All patients who receive any treatment will be included in the analyses of both efficacy and safety. Patients who are not evaluable for response will be considered non-responders. The final analysis will be an Intent to Treat analysis. A total of 60 patients will be enrolled at the rate of 3-4 patients per month. Stopping boundaries will be assessed in cohorts of 5 patients after a minimum of 10 patients have been enrolled. Response and toxicity will be monitored independently. The method of Thall and Simon will be employed to perform interim monitoring.

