##### **11.6.1 Primary Analysis**

The primary endpoint in this study is response defined as the percentage of subjects achieving a complete or partial tumor response using RECIST criteria. The response rate will be calculated from the view of best response that records confirmed cases of CR or PR. Subjects with unknown or missing response will be treated as non-responders; i.e., they will be included in the denominator when calculating the percentage. Response will be evaluated by the recist criteria 4 weeks (+/- 4 days) after completion of radiation therapy.

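### If the 4-week assessment in section 11.6.1 governs, a CR or PR first reached after new chemotherapy can count towards the primary response rate

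*Combined protocol and SAP*

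**What the plan says.** All references are to the combined protocol and SAP.

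- **Section 6.0, Study Design:** "Chemotherapy administered after protocol treatment (after the last dose of radiation and capecitabine) is acceptable". No minimum interval is given, and nothing ties the start of this chemotherapy to the response assessment.
- **Section 11.6.1, Primary Analysis:** "Response will be evaluated by the recist criteria 4 weeks (+/- 4 days) after completion of radiation therapy". The summary measure is a confirmed best response: "The response rate will be calculated from the view of best response that records confirmed cases of CR or PR". The only rule there on doubtful cases concerns absent data: "Subjects with unknown or missing response will be treated as non-responders".
- **Section 11.3, Sample Size Considerations and Interim Analyses,** gives a different time: "Tumour response will be assessed after 45 Gy". This is the section that introduces the stopping rules.
- **Section 9.1** takes a patient off study treatment if "Nonprotocol therapy (chemotherapy) is administered during study treatment". The rule is listed under the radiation period and does not reach the weeks after it.
- **Section 11.1** treats the regimen as worth further study "if the response rate is at least 80"% and grade III toxicity, leaving out acute skin reactions, is below 20%.

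**The concern.** The primary objective is the response to concurrent radiation with capecitabine. If section 11.6.1 sets the assessment, a patient may already be on a different systemic treatment when the deciding scan is taken. The confirming assessment, for which the available text gives no interval, may come later still. A patient who had not responded to the study regimen, but whom the new drug moves across the CR/PR threshold, would be counted as a success of the study regimen.

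The trial has one arm, so no comparison group shows how much of the response rate belongs to the later drug. The rate is read against a fixed threshold, and a few such patients near 80% could change the conclusion.

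**Working it through.** **Does the plan allow it?** Four weeks plus or minus 4 days is 28 − 4 = 24 to 28 + 4 = 32 days after radiation. Section 6.0 allows chemotherapy throughout that interval. Section 9.1 stops applying when treatment ends. Section 11.6.1 reclassifies only unknown or missing responses, and the evaluable-only analysis in section 11.6.2 removes only those patients. Neither deals with a response first seen after new therapy. The 45 Gy assessment in section 11.3 falls before the last dose, so this chemotherapy cannot affect it.

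**Reproducing the plan's figures.** Section 11.3.1 gives priors beta(1.6, 0.4) for response and beta(0.4, 1.6) for toxicity, with targets beta(80, 20) and beta(20, 80). With x events in n patients:

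- stop for response if Pr[beta(1.6 + x, 0.4 + n − x) < beta(80, 20)] > 0.95;
- stop for toxicity if Pr[beta(0.4 + x, 1.6 + n − x) > beta(20, 80)] > 0.925.

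All 11 response limits and all 11 toxicity limits match the table. An exact binomial recursion over looks at 10, 15, ..., 55, with response and toxicity independent, gives early stopping of 0.785 at true rates 0.65/0.10 and 0.084 at 0.80/0.10. The plan states 0.78 and 0.08. The design arithmetic is sound; the question is what the 4-week response measures.

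**Inputs for the illustration.**

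- From the plan: "A total of 60 patients will be enrolled at the rate of 3-4 patients per month"; success needs at least 0.80 × 60 = 48 responses and fewer than 0.20 × 60 = 12 toxicities, with no early stop.
- Assumed: response to the regimen alone p = 0.75, the same at 45 Gy and at 4 weeks; toxicity 0.10.
- Assumed: a share c of the regimen's non-responders converts on later chemotherapy. Here c is the share of them who start it before the assessment, times the share of those who convert.

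**Observed response rate:** q = p + (1 − p)c. For c = 0, 0.05, 0.10 and 0.20, q = 0.75, 0.7625, 0.775 and 0.75 + 0.25 × 0.20 = 0.80.

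**Two monitoring cases.**

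- *Monitoring on the 4-week response:* the recursion runs at q throughout.
- *Monitoring on the 45 Gy response:* the recursion runs at p. If R patients respond at 45 Gy, the final count is R + Binomial(60 − R, c).

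In both cases the response part is multiplied by the probability of at most 11 toxicities with no toxicity stop, which is 0.983.

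| c (assumed) | Observed rate | Success, 4-week monitoring | Early stop, 4-week monitoring | Success, 45 Gy monitoring | Early stop, 45 Gy monitoring |
|---|---|---|---|---|---|
| 0 | 75% | 0.22 | 0.25 | 0.22 | 0.25 |
| 5% | 76.25% | 0.30 | 0.20 | 0.29 | 0.25 |
| 10% | 77.5% | 0.38 | 0.15 | 0.37 | 0.25 |
| 20% | 80% | 0.56 | 0.08 | 0.52 | 0.25 |

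From a true 70%, c = 20% gives q = 0.70 + 0.30 × 0.20 = 0.76. The chance of success rises from 0.05 to 0.28 with 4-week monitoring, or to 0.24 with 45 Gy monitoring. In the latter case early stopping stays at 0.53.

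**The case against.** The strongest reply is that section 11.3 sets the design and puts the assessment after 45 Gy, and section 6.0 requires RECIST measurement on those images. On that reading the exposure disappears. This stands as a condition on the point but does not remove it: section 11.6.1 is headed as the primary analysis and names 4 weeks, and the two sections are not reconciled.

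Second, entrants' disease has largely progressed on, persisted through or barely responded to chemotherapy, so few may convert. This also stands. A c of 20% needs every non-responder to start early and 20% of them to convert, or half to start and 40% of those to convert. It is the top of the range shown, not a forecast.

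Third, Appendix F holds the RECIST rules and is not in the available text. It may bear on confirmation or on subsequent therapy, so the point is limited to what can be seen.

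A reader might also infer that the futility rule is weakened, with early stopping falling from 0.25 to 0.08. The documents do not support that as a general statement. It needs interim monitoring to use the 4-week response, and section 11.3 describes the 45 Gy assessment alongside the stopping rules. With 45 Gy monitoring, early stopping does not change.

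Nor does every bit of later shrinkage inflate the rate. Only shrinkage that takes a patient across the CR/PR threshold does.

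**Conclusion.** The gap is real but conditional. If section 11.6.1 governs, the plan lets a response first reached after other chemotherapy count for the study regimen, and no rule in the available text prevents it. If section 11.3 governs, this does not arise.

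The size cannot be known from the documents, which give neither the share of patients starting chemotherapy within four weeks nor their conversion rate. Under the assumptions above (true response 75%, toxicity 10%), conversion of 5 to 20% of non-responders raises the chance of meeting the criterion from 0.22 to between 0.29 and 0.56, depending on c and on which response drives monitoring. A reader might infer that the reported rate will be too high; the documents show only that it can be. The point is worth settling before analysis, because a result near 80% could not otherwise be clearly attributed to the regimen.

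**What to change.** 1. Reconcile the assessment time in sections 11.3 and 11.6.1, and say which response drives the interim monitoring.
2. State in section 11.6.1 that only assessments made before surgery and before any new systemic anti-cancer therapy count towards the primary response.
3. Record the start date of any such therapy.
4. For patients who start it before the 4-week assessment, use the last earlier on-study RECIST measurement, which is the post-45 Gy images. Say how the confirmation requirement applies to them, since a confirming scan before the new therapy may not exist.
5. Report a sensitivity analysis that includes the later assessments.

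The cost is a few sentences and one date field. The downside is that these patients are judged on a scan taken before radiation is complete, possibly a cone-beam or on-rails CT made to judge re-planning. This mixes timepoints within one endpoint and may understate late shrinkage; reporting both rates shows how much the conclusion depends on the choice. The change concerns what is counted, not when chemotherapy may be given.

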#### i. Efficacy

The secondary efficacy objectives of the study are:

- To determine the rate of conversion to operable, cCR, and pCR after completion of all protocol specified therapy. This includes the following:
  - Pre-operative concurrent radiation with capecitabine to the breast and at risk or involved regional lymph node basins
- To determine locoregional control of unresected nodal disease treated to definitive radiation dose ( $\geq 60\text{Gy}$ )

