## 8.0 Selection of Patients

### 1. 8.1 Inclusion Criteria

1. Histological confirmation of invasive breast cancer
2. No contraindications to receiving a course of radiation treatment (pregnancy, prior radiation to the volume with disease, or systemic disease in which radiation therapy is an absolute contraindication).
3. Patients who have chemo-refractory gross disease in the breast causing symptoms (pain, drainage, duress) OR

gross disease in the breast ( $\geq T3$ ) and/or lymph node(s) progressive, persistent, or minimally responsive to chemotherapy deemed inoperable or questionable inoperable  
OR

recurrent gross disease in a previously unirradiated breast or on the chest wall or in the regional lymphatics (core biopsy will not be offered to patients without gross disease in the breast).

4. Are able to swallow and retain oral medication (intact pill).
5. Age over 18.
6. Female gender

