##### **11.6.2 Secondary Analysis**

Patients who were deemed at time of enrolment to be inoperable or questionably inoperable (requiring flap closure with doubt regarding ability to obtain negative margins based on surgical oncology assessment) who have objective clinical response and receive mastectomy or are offered mastectomy but refuse will be considered having converted to operable. Patients who are resectable but considered inoperable based on advanced locoregional disease or M1 disease who have a mastectomy and no FDG-avid disease on PET at 3 month follow up will also be considered having converted to operable.

A secondary indicator of treatment efficacy is pCR. pCR is defined as the lack of any invasive disease in the breast and lymph nodes. A pathologist at the University of Texas M.D. Anderson Cancer Center will perform accurate sampling and review of all cases that have surgery. pCR will be assessed at the time of surgery following the completion of all protocol specified neoadjuvant chemotherapy, which will be approximately 26

weeks following the start of neoadjuvant chemotherapy. Subjects with unknown or missing response and those who do not convert to operable will be included in the primary efficacy analysis as non-responders.

A secondary analysis will calculate response rate based on subjects with evaluable tumor response only; i.e., the denominator will only include subjects with CR, PR, SD, or PD and will not include those with unknown or missing best response.

Exact 95% confidence limits for the clinical response rate will be calculated.

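### The conversion-to-operable rate has no denominator fixed at baseline, so failures can drop out of it and the rate can be biased upward

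*Combined protocol and SAP*

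**What the plan says.** **Scope.** The primary objective in Section 1.0 covers pre-operative or palliative treatment. The objective for conversion, cCR and pCR (Section 1.0, i. Efficacy) names only the first: "Pre-operative concurrent radiation with capecitabine to the breast and at risk or involved regional lymph node basins". Section 10.0 repeats that line and adds that the rates are taken among those who go to surgery.

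**Intent.** Section 6.0 records intent at the start: "Palliative vs pre-operative intent (based both on extent of metastatic disease and primary disease) will be recorded by the treating physician". For patients treated with pre-operative intent, "Surgical consultation or follow up will be requested to be scheduled after 45 Gy and before the final fraction of radiation". It then adds: "The treating oncologist may change this status to palliative if the clinical course makes the surgical consult unnecessary/patient is clearly unresectable".

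**Who counts as converted (Section 11.6.2).** The first route starts from "Patients who were deemed at time of enrolment to be inoperable or questionably inoperable", and of these, patients "who have objective clinical response and receive mastectomy or are offered mastectomy but refuse will be considered having converted to operable". The second route covers "Patients who are resectable but considered inoperable based on advanced locoregional disease or M1 disease who have a mastectomy" and whose PET shows no FDG-avid disease at three months.

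**Analysis sets.** Section 11.5 defines an intent-to-treat population (all treated patients) and a surgical population (operated patients only). Section 11.6 uses the first for the primary analysis and the second for a secondary analysis of surgical efficacy. Neither section assigns conversion by name. Section 11.6.2 sends non-converters, as non-responders, to the primary efficacy analysis, which Section 11.6.1 defines as RECIST response.

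**The concern.** A conversion rate describes treatment only if every patient who could have converted stays in the denominator. Two parts of the text let failures leave.

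First, the surgery restriction in Section 10.0 conditions on something close to the outcome. Most non-converters are never operated on, so they are not counted. It also does not fit the numerator: Section 11.6.2 credits a responding patient who is offered mastectomy and refuses, yet she is not among the operated.

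Second, if pre-operative in Sections 1.0 and 10.0 is read as current intent, the scope of the endpoint rests on a label that can be withdrawn because the patient is unresectable. Being unresectable is failing to convert, and the change is one physician's judgment in an open-label single-arm trial.

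The result is likely to be read beside the background figures in Sections 3.2 and 3.5: 32 of 38 (84%) operated after radiation, 91% of 55 converted on the proposed regimen, and 23 of 28 (82%) rendered operable. A rate that has lost its failures would look better than it should.

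**Working it through.** **The plan's own figures.** The documents give no target, power or planned rate for conversion, so there is no stated conversion figure to reproduce. The primary-endpoint figures do reproduce. All 11 response and 11 toxicity boundaries match. The intervals 81.1%–95.9% and 3.1%–16.8% follow from beta(55.6, 6.4) and beta(5.4, 56.6). The nine early-stopping probabilities agree within 0.01. None of these involves conversion.

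**Inputs.** The 60 planned patients come from Section 11.3. Everything else is assumed: D = 40 patients who are conversion candidates by enrolment status, C = 32 of them converted, and m non-converters relabelled palliative.

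**Formulas.** Enrolment denominator: C/D. Denominator following current intent: C/(D − m), an excess of C·m/[D(D − m)]. Operated patients only: C/C, if every converter and no non-converter is operated on.

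| Reading of the denominator | Calculation | Rate | Exact 95% CI |
|---|---|---|---|
| Status at enrolment (11.6.2) | 32/40 | 80.0% | 64.4–90.9 |
| Current intent, m = 2 | 32/38 | 84.2% | 68.7–94.0 |
| Current intent, m = 4 | 32/36 | 88.9% | 73.9–96.9 |
| Operated only (10.0) | 32/32 | 100% | 89.1–100 |

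**Sensitivity to the assumptions.** For D from 30 to 60 and true rates from 60% to 90%, dropping two relabelled failures adds about 2 points (36/60 = 60.0% to 36/58 = 62.1%) to 6 points (27/30 = 90.0% to 27/28 = 96.4%). Dropping five, where there are at least five, adds about 5 points (36/60 to 36/55 = 65.5%) to 16 points (24/30 = 80.0% to 24/25 = 96.0%).

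**Operated-only reading.** The 100% is a limit, not a certainty. A patient can have a mastectomy without an objective response, or fail the PET condition of the second route, and so be operated on but not converted. The mismatch over refusals is separate. If two of the 32 converters refused surgery, the Section 11.6.2 numerator over the Section 10.0 denominator is 32/30 = 107%, which is not a proportion.

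**Direction of the relabelling effect.**

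- Denominator follows current intent: the rate rises, as in the table.
- Operated only: an unoperated patient is already out, so relabelling her changes nothing.
- Enrolment status: the relabelled patient stays in. If she misses the consult at which mastectomy could be offered, relabelling can only lower the rate.

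**Pooling of enrolment groups.** Section 8.1 admits both kinds of patient: "responsive to chemotherapy deemed inoperable or questionable inoperable". If a share q is questionably inoperable and converts at an assumed 95%, and the rest convert at rate p, the pooled rate is (1 − q)p + 0.95q. For p from 60% to 80%, q = 25% gives 68.8% to 83.8%, about 4 to 9 points above p. With q = 50% it is 77.5% to 87.5%, about 8 to 18 points above p. This is a difference between target groups, not an estimation error.

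**The case against.** The strongest reply is that the sentence on changing intent concerns the scheduling of a consult and sets no analysis rule. No section removes a relabelled patient from anything. The first route in Section 11.6.2 is tied to status at enrolment, and Section 11.5 uses all treated patients for efficacy. Section 6.0 also says that eligible women receive pre-operative radiation, with no exception for palliative intent, and the second route lets M1 patients convert. So pre-operative may describe the treatment and not a subgroup by intent.

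This stands in part. A reader might infer that relabelled failures are excluded and that the rate is therefore biased upward as a matter of fact. The documents do not support that: the bias depends on a denominator they leave open. But Section 11.6.2 does not close the gap. It says who has converted and not out of whom, and its sentence on non-converters concerns the primary analysis. The surgery restriction may have been meant for pCR alone, but as worded it covers conversion too.

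A reader might also infer that counting questionably inoperable patients biases the rate. It does not. The group is defined in advance (flap closure needed and margins in doubt on surgical assessment), it is an intended entry group, and its members need an objective response plus mastectomy received or offered. Pooling affects interpretation only. Nor is a test against the background series planned, and the documents do not say whether those series included borderline cases.

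**Conclusion.** The conversion rate lacks a denominator fixed at baseline. One wording of the endpoint removes most failures and pushes the rate toward 100% by construction. Another can be read to follow a label that may change because of failure. In the example the same 32 conversions read as 80%, 84%, 89% or 100%. Those counts are assumptions; the text supports the direction and the dependence on an unmade choice, not a particular size. The claim is that the rate can be biased upward, not that it will be. On the enrolment reading there is no inflation. The weight is moderate: this is a secondary endpoint outside the stopping rules, and RECIST response and the sample size do not depend on it.

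**What to change.** - In Section 11.6.2, state the denominator: all treated patients judged at enrolment to be inoperable, questionably inoperable, or resectable but considered inoperable (locoregional extent or M1), whatever happens later to the recorded intent. Basing it on operability and not on intent keeps in the M1 patients whom the second route can credit.
- State that patients relabelled palliative or not operated on stay in and count as not converted, apart from responders who were offered mastectomy and refused, as the first route already provides.
- In Section 10.0, remove the surgery restriction from the conversion endpoint. Label any pCR rate in operated patients as conditional on surgery.
- Report conversion with exact 95% confidence intervals separately for the enrolment groups, as an aid to interpretation, and give the number and timing of changes of intent.
- Confirm that operability at enrolment is captured on the baseline form. Section 6.0 mentions the Initial Assessment Form in connection with intent, and the form itself is not in the text available.

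The cost is wording in two sections and possibly one form field. Clinical management does not change. The reported rate may be lower, and group-level intervals will be wide: 32/40 alone spans 64.4% to 90.9%.
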